8.3.8 Magnetic resonance imaging

Magnetic resonance imaging scans need to be reviewed locally for any pathology. In case of clinically significant findings, relevant information needs to be provided to the Treating Investigator for appropriate safety reporting and also to ensure the appropriate management of the participant's identified safety finding. When available, a diagnosis of pathology at cause of such MRI findings or the findings themselves will be reported as an AE until the diagnosis is clear.

Multiple sclerosis findings on MRI do not need to be reported unless they are deemed unusual and thus a distinct safety finding.

8.3.9 Adverse event of special interest

Adverse event of special interest

An AESI is an AE (serious or nonserious) of scientific and medical concern specific to the Sponsor's product or program, for which ongoing monitoring and immediate notification by the Investigator to the Sponsor is required. Such events may require further investigation in order to characterize and understand them. Adverse events of special interest may be added, modified, or removed during a study by protocol amendment.

- Pregnancy of a female participant entered in a study as well as pregnancy occurring in a female partner of a male participant entered in a study with IMP/NIMP
 - It will be qualified as an SAE only if it fulfills one of the seriousness criteria (see Appendix 3 [Section 10.3]),
 - In the event of pregnancy in a female participant, IMP should be discontinued,
 - Follow-up of the pregnancy in a female participant or in a female partner of a male participant is mandatory until the outcome has been determined (See Appendix 4 [Section 10.4]).

- Symptomatic overdose (serious or nonserious) with IMP
 - An overdose (accidental or intentional) with the IMP is an event suspected by the Investigator or spontaneously notified by the participant (not based on systematic pills count) and defined as at least twice the intended dose within the intended therapeutic interval (eg, ≥2 tablets of the IMP within a 12-hour interval).
- Increase in alanine transaminase (ALT) >3 × ULN
 - ALT increase >3 × ULN confirmed by retest within 72 hours or in the absence of a retest within 72 hours.

• Other project specific AESI(s)

- ECG observation of atrial fibrillation or atrial flutter,
- Severe infection (NCI CTCAE Grade 3 or above) infection, that may or may not meet seriousness criteria (eg, a Grade 3 opportunistic infection),
- Moderate or severe hemorrhagic events (NCI CTCAE Grade 2 or above), including but not limited to symptomatic bleeding, bleeding in a critical area or organ such as the CNS, or intraocular bleeding,
- Thrombocytopenia, platelet count <75 000/mm³ (see Appendix 6 [Section 10.6] for management flow chart).

8.3.10 Guidelines for reporting product complaints

Any defect in the IMP must be reported as soon as possible by the Investigator to the monitoring team that will complete a product complaint form within required timelines.

Appropriate information (eg, samples, labels or documents like pictures or photocopies) related to product identification and to the potential deficiencies may need to be gathered. The Investigator will assess whether or not the quality issue has to be reported together with an AE or SAE.

8.4 TREATMENT OF OVERDOSE

The Sponsor does not recommend specific treatment for an overdose.

In the event of an overdose, the Treating Investigator should do the following:

- 1. Contact the Sponsor immediately.
- 2. Closely monitor the participant for any AE/SAE and abnormal laboratory test values.
- 3. Obtain a plasma sample for PK analysis within 24 hours of the last documented IMP dose.
- 4. Document the quantity of the excess dose as well as the duration of the overdose in the eCRF.
- 5. Decisions regarding dose interruptions will be made by the Investigator in consultation with the Sponsor based in the clinical evaluation of the participant.

Amended Clinical Trial Protocol 12 SAR442168-EFC16645 - tolebrutinib 20-Dec-2023 Version number: 1

8.5 PHARMACOKINETICS

- Blood samples of approximately 2 to 3 mL will be collected for measurement of plasma concentrations of SAR442168 and relevant metabolite(s) as specified in the SoA (Section 1.3). The 5 scheduled samples will be collected at selected timepoints during the study (for participants who discontinued IMP, no PK samples are collected after pEOT visit). If warranted and agreed upon between the Investigator and the Sponsor, additional PK samples may be collected (eg, for retesting, pEOT, or if clinically indicated). The PK sample collection/storage is strongly recommended for events of confirmed ALT increase >5 × ULN (recommended for ALT >3 × ULN) and thrombocytopenia (platelets <75 000/mm³), and is recommended for events of neutropenia (neutrophils <1500/mm³), serum creatinine increase (confirmed increase >1.7 × ULN or decrease clearance >50%, cannot be rapidly reversed), and CPK increase (confirmed >10 × ULN) (see Section 10.6 for more details).
- Instructions for the collection and handling of biological samples will be provided by the Sponsor. The actual date and time (24-hour clock time) of each sample will be recorded.
- Each plasma sample will be divided into 2 aliquots (1 each for [PK, other analyses, and a back-up]). Samples collected for analyses of SAR442168 and relevant metabolite(s) plasma concentration may also be used to evaluate safety or efficacy aspects related to concerns arising during or after the study.
- Population PK analysis will be performed using SAR442168 and relevant metabolite(s) concentration and will be reported in a standalone report.

Drug concentration information that would unblind the study will not be reported to investigative sites or blinded personnel until the study has been unblinded.

8.6 PHARMACODYNAMICS

Blood samples for lymphocyte phenotyping will be collected during the study as detailed in the SoA (Section 1.3) for a subset of up to 200 randomized participants. Flow cytometry will be used for evaluation of change from baseline in lymphocyte count and phenotype in a subset of participants. Additional PD evaluations will include assessment of NfL levels in plasma, Chi3L1, and Ig levels in serum. For lymphocyte phenotyping, participants who did not have a baseline sample collected will no longer need to have this test performed; participants who had a baseline sample collected will have a second sample collected at EOT/pEOT. For additional PD evaluations (NfL levels and Chi3L1 and Ig levels), sample collections are no longer needed for participants who discontinued IMP or switched to other DMTs. For participants in China, see Appendix 7 (Section 10.7).

8.7 GENETICS

A 6 mL blood sample for DNA isolation will be collected from participants who have consented to participate in the genetic analysis component of the study. Participation is optional. Participants who do not wish to participate in the genetic research may still participate in the study. DNA samples will be collected during the study as detailed in the SoA (Section 1.3). Samples will be stored, and analysis may be performed on genetic variants thought to play a role in MS including, but not limited to, specific candidate genes/genome analyses to evaluate their association with observed clinical responses to SAR442168. For participants in China, see Appendix 7 (Section 10.7).

In the event of DNA extraction failure, a replacement genetic blood sample may be requested from the participant. Signed informed consent will be required to obtain a replacement sample unless it was included in the original consent.

8.8 **BIOMARKERS**

Blood samples for biomarkers research will be collected from all participants in this study as specified in the SoA (Section 1.3).

- Collection of plasma and serum samples for biomarker research is also part of this study.
- Samples will be tested to evaluate biomarkers and their association with the observed clinical responses to SAR442168.
- In addition, samples will be stored, and analysis may be performed on biomarker variants thought to play a role in MS including, but not limited to, plasma or serum analytes to evaluate their association with observed clinical responses to SAR442168.

Samples may be stored for a maximum of 2 years (or according to local regulations) following the last participant's last visit for the study at a facility selected by the Sponsor to enable further analysis of biomarker responses to SAR442168. For participants in China, see Appendix 7 (Section 10.7).

8.9 IMMUNOGENICITY ASSESSMENTS

Not applicable.

8.10 MEDICAL RESOURCE UTILIZATION AND HEALTH ECONOMICS

Health Economics/Medical Resource Utilization and Health Economics parameters are not evaluated in this study.

8.11 USE OF BIOLOGICAL SAMPLES AND DATA FOR FUTURE RESEARCH

Future research may help further the understanding of disease and the development of new medicines. Reuse of coded data and biological samples (leftover) will be limited to future scientific research conducted under a research plan for the purpose of diagnosing, preventing or treating diseases. The future research projects will be conducted under the Sponsor's and/or its affiliates' and/or, if applicable, the partner of the Sponsor which has licensed the study drug to the Sponsor or which is co-developing the study drug with the Sponsor's control, acting alone or in collaboration with research partners such as universities, research institutions or industrial partners with whom the coded data may be shared.

Data and biological samples will be stored and used for future research only when consented to by participants (see Section 10.1.3) and, when applicable, further information on the future research has been provided to the study participant, unless prohibited by local laws or IRBs/IECs (in such case, consent for future use of data/sample will not be included in the local ICF). The conditions for reuse will be adapted locally with the appropriate language in the ICF.

In any case, a specific consent will be collected for the performance of genetic analyses on leftover samples.

Data protection - Processing of coded clinical data

The study participant will be provided will all mandatory details of the data processing in Part 2 of the core ICF.

The Sponsor adopts safeguards for protecting participant confidentiality and personal data (see Section 10.1.4).

Use of leftover samples for future research

Remaining leftover samples will be used only after the study ends, ie, end of study as defined in the study protocol.

The study participant will be provided with all mandatory details of the use of the human biological samples (leftover) in Section 2 of the Core ICF.

Study participant data will be stored for up to 25 years for regulatory purposes and future research. Biological samples for future use will be stored for up to 25 years after the end of the study. Any samples remaining at the end of retention period will be destroyed. If a participant requests destruction of his/her samples before the end of the retention period, the Investigator must notify the Sponsor (or its contract organization) in writing. In such case, samples will be destroyed and related coded data will be anonymized unless otherwise required by applicable laws.

9 STATISTICAL CONSIDERATIONS

9.1 STATISTICAL HYPOTHESES

The null hypothesis for the primary efficacy endpoint of time to onset of 6-month CDP is that there is no treatment difference between SAR442168 and placebo, and the alternative hypothesis is that there is a between-treatment difference.

To strongly control the Type 1 error rate for the study, a hierarchical testing procedure will be applied at a 2-sided 5% significance level, ie, each hypothesis will be formally tested only if the preceding one is significant at the 5% level. If SAR442168 is significant for the primary endpoint, a selective set of secondary endpoints will be tested following the hierarchical testing procedure. The complete list of the secondary endpoints that will be adjusted for multiplicity with their testing order will be detailed in the statistical analysis plan prior to database lock or any interim analysis, if applicable. The study will be declared positive if the null hypothesis for the primary endpoint of 6-month CDP for SAR442168 versus placebo is rejected.

9.2 SAMPLE SIZE DETERMINATION

Approximately 1700 participants will be screened to achieve up to 1290 randomly assigned to study intervention (2:1 randomization ratio of SAR442168 to placebo). This study is planned as an event-driven trial based on 6-month CDP. The study will continue until approximately 288 events are projected to have occurred to provide 80% power to detect a 30% risk reduction in 6-month CDP with SAR442168 compared to placebo (2-sided α =0.05). The following assumptions were used for the calculations: 2-year placebo event rate of 23.6%; annual discontinuation rate of 10%; constant hazard rates using a log-rank test; estimated enrollment period of 24 months with last randomized participant followed for 24 months.

Actual recruitment and disability event rates may vary; therefore, it is possible to stop with a reduced sample size of around 1100 and still maintain study power by extending the duration of the trial, if needed, to reach approximately the same number of events. For example, it could be that the last randomized participant is followed for around 30 months instead of 24, if necessary. Additional recruitment of participants will not substantially reduce the trial duration. In any case, the power is based on the number of events, and the actual trial duration will be dependent on the observed placebo rate and treatment effect.

Note: "Enrolled" means a participant's, or their legally acceptable representative's, agreement to participate in a clinical study following completion of the informed consent process. Potential participants who are screened for the purpose of determining eligibility for the study, but do not participate in the study, are not considered enrolled, unless otherwise specified by the protocol.

Amended Clinical Trial Protocol 12 SAR442168-EFC16645 - tolebrutinib 20-Dec-2023 Version number: 1

9.3 POPULATIONS FOR ANALYSES

For purposes of analysis, the following populations are defined (Table 3):

Population	Description
Enrolled	All participants who sign the ICF
Randomly Assigned to Study Intervention	All participants with a treatment kit number allocated and recorded in the IRT database, regardless of whether the treatment kit was used or not.
	Participants treated without being randomized will not be considered randomized and will not be included in any efficacy population.
ΙΤΤ	The primary efficacy population will be the ITT population, defined as all randomly assigned participants. All efficacy analyses will be conducted according to the treatment group allocated by the randomization schedule, irrespective of the treatment received.
Safety	All participants randomly assigned and exposed to study intervention, regardless of the amount of exposure, analyzed according to the treatment actually received.
	Randomized participants for whom it is unclear whether they took the study medication will be included in the safety population as randomized.
	The pharmacodynamic (PD) analyses will be performed on the safety population.
Pharmacokinetics	All participants in the safety population with at least one non- missing PK sample after first dose of the study intervention. Participants will be analyzed according to the treatment actually received.

Table 3 - Populations for analysis

ICF: informed consent form; ITT: intent to treat; PK: pharmacokinetic(s).

9.4 STATISTICAL ANALYSES

The SAP will be developed and finalized prior to database lock or before any interim analysis, if applicable, and it will include a more technical and detailed description of the statistical analyses described in this section. This section is a summary of the planned statistical analyses of the most important endpoints including primary and key secondary endpoints.

9.4.1 General considerations

The baseline value of efficacy parameters is generally defined as the last available value up to randomization but prior to the first dose of study medication unless otherwise specified. For EDSS, the baseline value will be taken as the average of the screening and randomization visit values. The baseline value of safety parameters is defined as the last available value prior to the first dose of IMP. Unless otherwise indicated, all statistical hypotheses for the primary and secondary endpoints and other treatment comparisons will be tested at the 5% significance level (α =0.05) against 2-sided alternatives.

9.4.2 Primary endpoint

The primary estimand will be the treatment difference between SAR442168 and placebo in time to onset of 6 month-CDP regardless of completion of the treatment period. This estimand corresponds to a "treatment policy strategy". This estimand will be considered primary for supporting regulatory decision making.

The time to onset of 6-month CDP will be analyzed by a Cox proportional hazards model with terms for treatment, age at screening (>40, \leq 40 years), geographic region (US, non-US), baseline EDSS score, and baseline Gd-enhancing T1 lesions (0, \geq 1). A log-rank test stratified by age at screening (>40, \leq 40 years) and geographic region (US, non-US) to compare SAR442168 to placebo will also be examined. Kaplan-Meier plots of the cumulative incidence rate will be provided by treatment group to depict the course of onset of 6-month CDP over time. The proportion of participants with events at given time points (eg, Month 24) will be calculated using the KM estimates.

In this primary ITT analysis:

- For participants who complete the study without an initial disability progression, the participant's event time will be censored at the date of last EDSS assessment.
- For participants who have an initial onset of disability progression but complete the study at the common study end date without 3-month confirmation, the participant will be censored at the date of last EDSS assessment.
- For participants who prematurely discontinue the study before 6-month confirmation of an onset of disability progression, regardless of having an initial onset, the participant will be censored at the date of last EDSS assessment.
- For participants who meet 3-month CDP but complete the study at the common study end date without 6-month confirmation, the event status of the participant will be determined by an imputation approach only if all additional EDSS assessments after 3-month confirmation to participant's end of study also meet the criteria for disability progression. Since in this setting, the partial missing data can reasonably be assumed to be missing at random, this approach leverages the partial information and follows the ITT principle. A logistic model with terms for age at screening (>40, ≤40 years), geographic region (US, non-US), baseline EDSS score, and baseline Gd-enhancing T1 lesions (0, ≥1) will be used to determine the event status as the imputation model within each treatment. A multiple imputation approach will be used to summarize the results. Details will be provided in the SAP.

Only EDSS assessments measured more than 90 days after the onset of an adjudicated relapse will be used to determine onset of disability progression. In addition, for the purpose of confirmation, only EDSS scores measured more than 90 days after the onset of an adjudicated relapse will be used. In case of such MS relapse, the next quarterly EDSS assessment >90 days after relapse onset will be used for CDP confirmation. In order to assess robustness of the primary analysis, sensitivity analyses handling missing or incomplete data differently will be conducted. This will include an analysis that treats missing or incomplete data as censored data.

Amended Clinical Trial Protocol 12 SAR442168-EFC16645 - tolebrutinib 20-Dec-2023 Version number: 1

Additionally, subgroup analyses will be explored to assess consistency of treatment effect. The subgroup factors include geographic region (US, non-US; Eastern EU, Western EU, North America, Rest of the World), age strata (ie, age at screening; >40, \leq 40 years), sex (male, female), baseline Gd-enhancing T1 lesions (0, \geq 1), baseline EDSS score (\leq 4.5 versus >4.5 and \leq 5.5 versus >5.5), prior disease modifying therapy use (0, 1, \geq 2), duration since RRMS symptom onset (\leq 5, >5 to \leq 10, >10 years) and adjudicated relapse during the study. The detailed list of subgroups and additional details of the subgroup analyses will be provided in the SAP.

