#### In this primary ITT analysis:

- For participants who complete the study without an initial onset of disability progression, the participant will be censored at the date of last EDSS assessment.
- For participants who have an initial onset of disability progression but complete the study without 3-month confirmation, the participant will be censored at the date of last EDSS assessment.
- For participants who prematurely discontinue the study before 6-month confirmation of an onset of disability progression, regardless of having an initial onset, the participant will be censored at the date of last EDSS assessment.
- For participants who complete the study, meet 3-month CDP criteria, and continue to meet criteria for EDSS disability progression through the final study assessment, but do not reach 6-month confirmation, the 6-month CDP event status of the participant will be determined by an imputation approach. The details of this imputation approach are provided in Section 3.2.3.

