#### **Analytical Approach**

The time to onset of 6-month CDP will be modeled by a Cox proportional hazards model with robust variance estimation (1). The covariates included in the model are treatment group, age at screening (>40,  $\leq$ 40), region (US, non-US), baseline EDSS score and baseline gadolinium (Gd)-enhancing T1 lesions (present, absent). The hazard ratio, its 95% confidence interval and the p-value for comparing tolebrutinib to placebo will be estimated from this model. Comparison between tolebrutinib and placebo will also be assessed by a log-rank test stratified by age at screening (>40,  $\leq$ 40 years) and region (US, non-US). Kaplan-Meier (KM) plots of the cumulative incidence rate will be provided by treatment group to depict the course of onset of 6-month CDP over time. The proportion of participants with events at given time points (eg, Months 6, 12, 18, 24, 30, ...) and median time to 6-month CDP will be calculated using the KM estimates.

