### 3.3.1.2 Main analytical approach

#### 3.3.1.2.1 Time to event endpoints

Time to onset of 3-month CDP will be analyzed using the same statistical methods as for the primary analysis of time to onset of 6-month CDP without imputation.

Time to onset of sustained 20% increase in the 9-HPT (T25-FW) for at least 3 months and time to onset of 6-month confirmed disability improvement (CDI) will be analyzed using similar statistical methods as for the primary analysis of time to onset of 6-month CDP, but without imputation. Participants with onset without confirmation will be treated as censored at the last endpoint assessment.

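### Participants stay at risk up to their last EDSS although a late onset can no longer count, so the planned Kaplan-Meier risks of 6-month CDP are too low; the hazard ratio moves only if study dropout differs by arm

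*Protocol*

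**What the plan says.** Protocol 9.4.2 and SAP 3.2.2 set the censoring date of the primary analysis. A completer (someone who reaches the common study end) with an onset lacking 3-month confirmation is censored at the last EDSS: in the protocol, such participants who "complete the study at the common study end date without 3-month confirmation, the participant will be censored at the date of last EDSS assessment"; in the SAP, "For participants who have an initial onset of disability progression but complete the study without 3-month confirmation, the participant will be censored". The same date applies more widely to those who leave the study: "For participants who prematurely discontinue the study before 6-month confirmation of an onset of disability progression, regardless of having an initial onset". Completers with no onset are also censored at the last EDSS.

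There are two exceptions. A completer who has met 3-month CDP and stays progressed to the final assessment has the 6-month status multiply imputed (SAP 3.2.3). Death due to MS counts as progression without confirmation (SAP 3.2.2, Death).

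SAP 3.2.1 dates a confirmed event back to its onset and requires at least 154 days to confirmation. SAP 3.3.1.1 requires at least 70 days for 3-month confirmation.

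Kaplan-Meier risks are planned outputs. Protocol 9.4.2: "The proportion of participants with events at given time points (eg, Month 24) will be calculated using the KM estimates". SAP 3.2.2: "The proportion of participants with events at given time points (eg, Months 6, 12, 18, 24, 30", with the list running on from there.

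For 9-HPT, T25-FW and CDI, SAP 3.3.1.2.1 says "Participants with onset without confirmation will be treated as censored at the last endpoint assessment". That section analyses 3-month CDP with the primary methods. None of the four uses imputation.

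**The concern.** Near the end of follow-up the analysis keeps people in the denominator while no onset of theirs can enter the numerator. Someone whose sustained progression begins in that stretch is carried as event-free beyond the onset. Entry is staggered and the study end is common, so the share of each late risk set that is in such a stretch grows with time, and the curves flatten for a reason unrelated to the disease. Dropout need not be related to disability for this to happen.

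The absolute risks by treatment group, and the difference between them, would be reported too low. A second worry is the hazard ratio. The blind stretch is about twice as long for a discontinuer as for a completer, so an arm that loses more participants has its hazard understated more.

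**Working it through.** **1. The plan's own figure.** Protocol 9.2 states that "approximately 288 events are projected to have occurred to provide 80% power to detect a 30% risk reduction in 6-month CDP with SAR442168", with 2:1 allocation and two-sided 0.05. Power = Φ(√(D·p·(1−p))·|ln HR| − 1.96). √(288 × 2/3 × 1/3) = √64 = 8; 8 × 0.3567 = 2.853; 2.853 − 1.96 = 0.893; Φ = 81.4%. The stated 80% is reproduced (278 events would give exactly 80%). The standard error of log HR is 1/8 = 0.125.

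**2. Hazards and true risks.** Protocol 9.2 gives a 2-year placebo event rate of 23.6%, so the hazard is −ln(1 − 0.236)/2 = 0.1346 per year; tolebrutinib 0.70 × 0.1346 = 0.0942. With the 28-day month (Protocol 4.1), true placebo risk = 1 − exp(−0.1346 × 28m/365.25): 21.9% at Month 24 (672 days), 31.0% at Month 36 (1008 days), 35.2% at Month 42 (1176 days).

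**3. When an onset can count for 6-month CDP.**

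| Time from onset to last EDSS | Completer | Premature discontinuer |
|---|---|---|
| 154 days or more | event | event |
| 70 to 153 days | imputed | censored at last EDSS |
| under 70 days | censored at last EDSS | censored at last EDSS |

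**4. Simulation.** Uniform accrual over 24 months and common end at 48 months (28-day months), quarterly EDSS plus an end-of-study EDSS, exponential onsets detected at the next visit, every onset sustained, dropout independent of progression. Completers in the imputation zone are counted as events. At least 400,000 participants per arm; Monte Carlo error about 0.1 to 0.2 points for risks and 0.003 for the HR.

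Placebo Kaplan-Meier risk, plan versus truth:

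| Dropout per year, both arms | Month 24 | Month 36 | Month 42 |
|---|---|---|---|
| none | 21.6% vs 21.9% | 29.4% vs 31.0% | 32.2% vs 35.2% |
| 10% | 20.7% vs 21.9% | 28.2% vs 31.0% | 30.9% vs 35.2% |

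With no dropout, the Month 42 risk difference reads 8.3 points instead of 9.0. At 10% dropout about 36 sustained onsets per 1290 participants are seen but carried as event-free, roughly 23 in completers and 13 in discontinuers. A longer, calendar-month timeline gives nearly the same picture: plan 21.0%, 28.7% and 31.8% at the three time points. Ending time at risk at the last EDSS from which an onset could still count brings the estimates within about 0.2 points of the truth.

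**5. Hazard ratio (true value 0.70).** With 10% dropout in both arms the plan gives 0.703, so there is no shift. The documents give one dropout rate, not split by arm; the splits below are assumptions.

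| Dropout, placebo / tolebrutinib | Plan | SAP sensitivity 1 | Earlier censoring |
|---|---|---|---|
| 8% / 12% | 0.689 | 0.703 | 0.703 |
| 8% / 16% | 0.673 | 0.701 | 0.701 |
| 12% / 8% | 0.719 | 0.703 | 0.704 |

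On the log scale the first row is ln(0.703/0.689)/0.125 = 0.16 standard errors and the second ln(0.701/0.673)/0.125 = 0.33.

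**6. Secondary endpoints.** Without imputation the blind stretch is about 70 days for 3-month CDP, 9-HPT and T25-FW, and 154 days for CDI, whoever the participant is. The documents give no event rates for these, so no size is put on it. All four are in the testing sequence of SAP 3.5.

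**The case against.** The strongest reply is that SAP 3.2.4 already covers this. Its first sensitivity analysis counts every potential onset whose confirmation is missing, in the same Cox model. In the simulation it removes the hazard-ratio shift as well as earlier censoring does. That stands, with two limits: it also counts onsets that would have proved transient, so with real data it is a bound and not a correction, and only Cox results are planned for it, not Kaplan-Meier estimates. The second sensitivity analysis does not help. It censors at the same last EDSS without imputation, so it has the same bias and a larger Kaplan-Meier shortfall.

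It is also fair to say that the curves are descriptive, that the primary conclusion rests on the Cox test, and that the largest gaps lie where few are followed. Under 24 + 24 months, (48 − 42)/24 = 25% of participants can reach Month 42. At Month 24, the protocol's own example, the gap is about 1 point with 10% dropout and 0.3 points with none.

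A reader might infer that the plan biases the primary hazard ratio. The documents do not support that: they give a single 10% rate, under which there is no shift. Participants who stop study drug are asked to stay to the end of the study (Protocol 7.1.1), so unequal tolerability need not become unequal study dropout. Nor are participants censored because they progressed: the censoring date is the last EDSS with or without a late onset. The defect is that late onsets are not ascertained while time at risk continues.

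Finally, the version history of the SAP and the log for protocol amendment 10 show that the censoring and imputation rule was revised on regulatory feedback. Replacing it as the primary rule would be a trade-off, not a correction.

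**Conclusion.** The Kaplan-Meier curves and time-point proportions of 6-month CDP are biased low in both arms. With 10% annual dropout the placebo shortfall is about 1 point at Month 24, 3 points at Month 36 and 4 points at Month 42.

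The primary hazard ratio is unaffected when study dropout is equal by arm. If it differs, the ratio moves in favour of the arm losing more participants, by about 0.015 for 8% versus 12% and about 0.03 for 8% versus 16%. The direction cannot be known in advance; heavier placebo loss would make the result conservative. Power is not in question, since the trial is event-driven.

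The sizes rest on the Protocol 9.2 assumptions, on all onsets being sustained and on dropout unrelated to progression. Informative dropout could change the size or the direction.

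**What to change.** Keep the last-EDSS rule for the primary Cox test. For the Kaplan-Meier curves and time-point proportions of 6-month CDP, and for one added prespecified Cox sensitivity analysis, end time at risk for participants without a counted event at the last EDSS that has at least 70 days (completers) or 154 days (premature discontinuers) of later EDSS follow-up.

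State how MS deaths are handled there, because they count without confirmation. One consistent choice is not to count a death whose event date falls after that participant's truncated censoring date; retaining such deaths would introduce an opposite, probably small, bias.

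For the secondary endpoints use 70 days (3-month CDP, 9-HPT, T25-FW) and 154 days (CDI). Report study dropout by arm, separately from discontinuation of study drug.

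The cost is SAP wording and one more derived date. No confirmed or imputed event is lost, apart from any MS death set aside in the supplementary analysis. The curves end about 12 weeks earlier and late numbers at risk are smaller.
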